**Table 2. Sample size required to achieve 80% power using the proposed analysis**

Number of clusters (health facilities)	Sample size per cluster	Total sample size
1	--	--
2	--	--
3	--	--
4	--	--
5	496	2 480
6	113	678
7	68	476
8	51	408
9	37	333
10	30	300

Not all suspected malaria patients test positive for falciparum malaria. Therefore, to calculate the number of suspected *P. falciparum* cases to enroll, these numbers should be divided by the expected positivity rate. For example, if 40% of suspected *P. falciparum* cases are expected to come back positive, then the sample of 30 positive cases per cluster increases to 75 (30/0.4) suspected cases to enroll. This number should be further buffered to account for potential drop-out, e.g. due to sequencing failure or diagnostic accuracy. Finally, sample sizes may differ from one health facility to the next; the power of study designs with variable cluster sizes can be explored in the DRpower software and interactive web app (<https://shiny.dide.ic.ac.uk/DRpower-app/>).

## 5.5 Sampling

There is evidence that the prevalence of *pfhrp2/3* deletions may vary due to transmission intensity, and so countries are advised to establish transmission strata prior to selecting domains. Multiple domains may then be selected per stratum, aiming for good geographical spread. Depending on surveillance goals, it may be desirable to sample more domains from areas with greater population density.

Sampling in each domain can be via cluster randomization or sentinel surveillance. In the cluster randomized approach, a complete list of health facilities in the domain (e.g. province/district) should be compiled, and 10 health facilities should be sampled from this list using a random procedure. In the sentinel surveillance approach, 10 health facilities can be chosen deliberately, e.g. based on logistical feasibility, while striving to achieve a representative sample of the population.

Once health facilities have been selected, historical incidence trends can be used to establish the time frame over which the requisite samples can be obtained. This may lead to a variable sample size per health facility, which is valid as long as the overall study power is still 80% or higher (see interactive web app: <https://shiny.dide.ic.ac.uk/DRpower-app/>).

## 5.6 Data collection and fieldwork

The following general steps for data collection will be followed. **(Note that it will be necessary for each country to develop a specific standard operating procedure in order to tailor these steps to its particular context and needs.)**

The national malaria programme should identify the domains to be surveyed. A sampling domain can be a province, district, state or other unit, depending on the administrative boundaries of the country. This selection should be guided by an assessment of which domains may be most at risk for *pfhrp2/3* gene deletions; otherwise, domains can be randomly selected based on epidemiological zones. Domains with low, moderate and high transmission should be considered, whereas domains without malaria transmission should be omitted. The sample sizes may be reached more quickly in moderate to high transmission areas; however, the expected higher prevalence of multiclonal infections may mask the presence of *pfhrp2/3*-deleted parasites. This issue is less likely in low transmission areas and therefore these zones should be included.

1. Select a specified number of public health facilities (aiming for 10) in each domain of the country routinely using malaria RDTs to be included in the survey.
  - The number of facilities per domain to be included in the sample should take into account the expected mean number of suspected *P. falciparum* cases seen in the facility each week and the mean test positivity rate in the target area in order to ascertain the expected number of positive cases each week. As a general rule, the aim is to finish the fieldwork and collect a minimum sample size of 300 positive cases within an eight-week period (assuming 10 health facilities are selected; if the number of health facilities is reduced, a higher sample size will be required, as explained in section 5.4).
  - Health facilities for the sample should be selected from a complete list (sampling frame) of health facilities in each domain, using systematic random sampling based on probability proportional to size (28) (and proportional to the size of the facility type strata in each domain). The sampling frame must include some estimate of facility size (fever or suspected malaria case load) and type (e.g. public, private, level, etc.).
  - *Note:* if budgetary or logistical constraints preclude the selection and inclusion of facilities using random sampling, a purposeful (or convenience) sample of facilities can be used. However, it should then be noted that domain-level estimates of *pfhrp2/3* gene deletions may not be statistically representative of the domain. If convenience sampling is conducted, efforts should be made to ensure that the sites are representative of the domain as a whole; otherwise, results will not have good external validity.
2. Survey procedures and analysis of data
  - Patients are triaged according to normal procedures. Any patient considered by the routine health provider, e.g. physician or nurse, to be a suspected malaria case according to national guidelines will be asked for consent/assent (Annexes 4 and 5).
    - Only consenting individuals will sign their name and be given a copy of the information sheet with their survey/sample ID in case they change their mind and wish to not participate in the future or wish to have samples removed from storage.

- Consenting patients will be asked a series of questions relevant to their illness and tested simultaneously according to the manufacturers' instructions for use by two separate diagnostics: the HRP2-based RDT used in the national control programme and either a Pf-LDH RDT or microscopy. A minimum of two DBSs will be collected on filter paper/protein saver cards.
- Non-consenting patients will receive routine care, and no record of their name or identity will appear on any survey documents. The blank non-consent form will be assigned a unique ID to allow for monitoring of the total number of consenting and non-consenting suspected malaria cases attending the facility on the survey tally sheet (Annex 6). All informed consent forms will be kept in a secure location under lock and key.
- The HRP2 and Pf-LDH RDTs will meet WHO procurement criteria and have approval for use by the Ministry of Health.
  - A Pf-LDH RDT that meets WHO procurement criteria (Table 3) or microscopy can be used for the secondary diagnosis. Currently, there are no RDTs that meet the WHO performance criteria for detection of *P. falciparum* based on their Pf-LDH test line alone (29); therefore, for the purposes of screening patients in the survey, countries may exceptionally select Pf-LDH-based RDTs that (i) have been evaluated in WHO malaria RDT product testing; ii) meet performance criteria for detecting HRP2-expressing *P. falciparum*; and (iii) have a panel detection score (PDS) > 90 at 2000 parasites/μL, and false-positive and invalid rates < 2% (see Table 4).
  - If microscopy is to be used, one thin and one thick blood film should be prepared following national guidelines and aligned with the WHO standard operating procedures for malaria microscopy (30).

**Table 3. WHO-recommended malaria RDT options for detecting both HRP2-expressing and non-expressing *P. falciparum* malaria for *pfhrp2/3* gene deletion surveillance**

Performance criteria	A: P. falciparum PDS a ≥ 75% at 200 parasites/μL
	B: P. vivax PDS a ≥ 75% at 200 parasites/μL
	C: false-positive (FP) rate against clean negatives < 10%
	D: invalid rate (IR) < 5%
	E: pfhrp2 -negative P. falciparum PDS > 75% at 200 parasites/μL (in areas where pfhrp2 deletions are prevalent)

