## Data collection

1. Identify domains (e.g. provinces, districts) to be included in the study. Factors to consider include: (i) capturing a range of transmission strata, (ii) ensuring broad geographical representation, and (iii) optionally, weighting based on population at risk.
2. Select 10 health facilities per domain for testing (if this is not possible, a smaller number of health facilities may be viable; see Table 2 for variations in the number of health facilities and recommended sample numbers). Any facility in which RDTs are being used is eligible; microscopy services are not a requirement. Selection of health facilities may be through randomization or deliberate choice (e.g. sentinel surveillance), and must ensure balanced representation of the target population.
3. In the target population (suspected malaria cases), conduct routine case management procedures and obtain informed consent (or assent, depending on the age of majority and federal guidelines in the country of enrolment) to perform an additional RDT and collect at least two dried blood spots (DBSs) for laboratory analysis and for biobanking/long-term storage to support future malaria epidemiological and diagnostic research.
4. Take clinical history, including questions regarding age, sex, recent malaria diagnostic testing, antimalarial therapy and travel.
5. Test all consenting suspected malaria cases simultaneously using both a WHO-recommended HRP2 RDT and a non-HRP2-based method (e.g. Pf-LDH RDT (separate single or multiple test line RDT)) or quality-assured microscopy in the health facility, and collect a minimum of two DBSs on filter paper or protein saver cards.
6. Record demographic and clinical history details and all test results on the survey report form.
7. Administer antimalarial therapy based on results from (either) RDT and/or microscopy, according to national guidelines.
8. Retain used RDTs for quality control and a minimum of two DBSs from all consenting *P. falciparum* patients for molecular +/- serological analysis.
9. Enrolment can stop once 30 individuals with confirmed *P. falciparum* malaria from each of 10 health facilities have been recorded in the survey tally sheet as having *P. falciparum* (a different number of confirmed individuals is required per health facility if using other than 10 clusters; see Table 2).
10. Ship all consent forms, tally sheets, survey report forms and patient samples to the central coordinating centre.

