## 5.2 Primary output indicators

The following indicators will serve as the primary survey outputs:

1. prevalence of false-negative HRP2 RDT results caused by *pfhrp2/3* gene deletions among all symptomatic *P. falciparum* confirmed cases;
2. prevalence of suspected false-negative HRP2 RDT results (i.e. a negative HRP2 RDT result but a positive result by Pf-LDH RDT or *P. falciparum* microscopy, or HRP2-negative but Pf-LDH-positive in a serological test) among symptomatic patients with *P. falciparum* malaria; and
3. prevalence of *pfhrp2/3* gene deletions among symptomatic falciparum patients with a false-negative HRP2 RDT result.

The survey will identify the proportion of patients with suspected false-negative HRP2 RDT results through diagnostic testing at health facilities, using dual-method testing (HRP2 RDT plus microscopy or Pf-LDH RDT). To save time and resources, molecular +/- serological testing to confirm *P. falciparum* infection and identify *pfhrp2/3* deletions will prioritize DBSs collected from individuals with suspected false-negative HRP2 RDT results. Discordant diagnostic results may be due to other factors, such as false-positive Pf-LDH test lines (possibly due to cross-reactivity with non-falciparum species) or low parasite densities at

---

1 RDTs should be used that contain Pf-LDH-specific test lines and not pan-pLDH test lines. This will ensure that only *P. falciparum* infections are detected and avoid the identification of non-falciparum species (*P. vivax*, *P. malariae*, *P. ovale*), which would cause discordant results (HRP2-negative, pan-pLDH-positive).

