## Annex 3. Mathematical details of the DRpower model used for sample size estimate

### Estimating if the prevalence of false-negative HRP2 RDT results caused by *pfhrp2/3* deletions is above a given threshold

The DRpower software implements a Bayesian model of *pfhrp2/3* deletion prevalence. The Bayesian framework has several advantages, including incorporating prior information and propagating uncertainty in a principled way. The model itself is a random effects model (1) in which cluster-level prevalence is assumed to vary around the global prevalence ( $p$ ) according to a beta distribution. The spread around this global prevalence is dictated by the intra-cluster correlation coefficient (ICC), denoted by  $r$ . A large value of  $r$  implies a wide spread of values because clusters have high correlation within them leading to overdispersion.

Mathematically, we can write:

$$X_i \sim \text{Beta}(\alpha, \beta), \quad (\text{A1})$$

where  $\alpha = p(\frac{1}{r} - 1)$ ,  $\beta = (1 - p)(\frac{1}{r} - 1)$ ,

where  $X_i$  is the prevalence in cluster  $i$ . The raw counts of the number of deletions in each cluster ( $k$ ) are modelled as binomial, with the number of trials given by the total sample size in that cluster ( $n$ ), and with the probability of success given by the cluster-level prevalence ( $X_i = x_i$ ). The combination of the beta random effects distribution with the binomial distribution means that counts follow an implied beta-binomial distribution. The probability mass function of this distribution can be written as:

$$\Pr(k|n, p, r) = \binom{n}{k} \frac{B(k_i + \alpha, n_i - k_i + \beta)}{B(\alpha, \beta)}, \quad (\text{A2})$$

where  $B(x, y)$  is the beta function. The likelihood over all  $c$  clusters is the independent product of (A2):

$$\Pr(\mathbf{k}|\mathbf{n}, p, r) = \prod_{i=1}^c \Pr(k_i|n_i, p, r). \quad (\text{A3})$$

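### Selecting facilities by suspected-case load and then taking a fixed 30 confirmed cases makes the sample self-weighting for suspected cases, while output 1 and the 5% rule are defined on confirmed P. falciparum cases

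*Protocol*

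**What the plan says.** Protocol section 5.6, step 1, asks for systematic random selection of facilities with probability proportional to size, and defines size in the frame: "The sampling frame must include some estimate of facility size (fever or suspected malaria case load) and type". The summary's data collection steps then fix the take: "Enrolment can stop once 30 individuals with confirmed *P. falciparum* malaria from each of 10 health facilities have been recorded". The Annex 6 tally sheet repeats the target of 30 per facility.

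The quantity to be estimated is in section 5.2: "prevalence of false-negative HRP2 RDT results caused by *pfhrp2/3* gene deletions among all symptomatic *P. falciparum* confirmed cases". Section 5.4 applies the 5% threshold to that same proportion. In Annex 3, "cluster-level prevalence is assumed to vary around the global prevalence", and the likelihood is a plain product over clusters. No section gives a design weight.

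On transmission, section 5.5 says that deletion prevalence "may vary due to transmission intensity, and so countries are advised to establish transmission strata prior to selecting domains". Section 5.6 adds that multiclonal infections in moderate to high transmission areas may hide deleted parasites, and that this is less likely in low transmission areas.

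**The concern.** Probability-proportional-to-size selection with a fixed take is self-weighting for whatever unit measures size. Here that unit is the fever or suspected case, whereas the stated denominator is the confirmed P. falciparum case. A facility with many fevers but few malaria cases is as likely to be drawn as one with the same fevers and many malaria cases. Each contributes 30 confirmed cases, so cases at the low-positivity facility are over-represented.

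This is harmless if positivity is unrelated to deletion prevalence across the facilities of a domain. If they are related, DRpower compares a different mean with 5%. Outcome 2 in any one domain leads to a recommended nationwide change of RDT (section 5.6, step 10), so a shift of the tested mean near 5% matters in either direction.

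**Working it through.** **Weighting.** Let S_i be the suspected load of facility i and q_i its test positivity, so it has S_i × q_i confirmed cases. The chance that a confirmed case enters the sample is proportional to

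S_i × 30 / (S_i × q_i) = 30 / q_i.

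Suspected load cancels and positivity does not. With size S_i × q_i, the same product is the constant 30.

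**Check of the model.** The Annex 3 model was coded as written: beta-binomial likelihood, uniform prior on p, Beta(1,9) prior on the ICC, numerical integration, and Outcome 2 if Pr(p > 5%) ≥ 0.95. Each setting had 1,500 to 4,000 simulated surveys (Monte Carlo error at most about 1 point). At 10% prevalence and ICC 0.05 it gives 80.6% power for 10 × 30, 81.0% for 9 × 37, 80.4% for 8 × 51, 80.0% for 7 × 68 and 79.4% for 6 × 113. Table 2 is reproduced.

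**Baseline.** At exactly 5% with no link, Outcome 2 occurs in about 6–9% of surveys. This, not 5%, is the comparator.

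**Assumed domains.** There are two groups of facilities, each with half the suspected load, positivity q_L and q_H, and prevalence d_L and d_H of deletion-caused false negatives. The low-positivity group's share of confirmed cases is w = q_L / (q_L + q_H). The value d_H is chosen so that w × d_L + (1 − w) × d_H = 5%. The mean under test is (d_L + d_H) / 2. The protocol gives no spread of positivity or prevalence between facilities, so all of these are assumptions.

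| q_L v q_H | w | d_L v d_H | Case-weighted prevalence | Mean under test | Outcome 2, size = suspected load | Outcome 2, size = confirmed load |
|---|---|---|---|---|---|---|
| 30% v 40% | 3/7 | 6% v 4.25% | 5.0% | 5.125% | 7–10% | not needed |
| 30% v 40% | 3/7 | 8% v 2.75% | 5.0% | 5.375% | 7–10% | not needed |
| 20% v 40% | 1/3 | 8% v 3.5% | 5.0% | 5.75% | 14–15% | 6–8% |
| 15% v 45% | 1/4 | 10% v 3.33% | 5.0% | 6.67% | 25–32% | 4–7% |
| 10% v 40%, reverse link | 1/5 | 2% v 5.75% | 5.0% | 3.875% | 1.3% | 7.8% |

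For the 15% v 45% row: 0.25 × 10% + 0.75 × 3.33% = 5.0%, and (10% + 3.33%) / 2 = 6.67%. Ranges cover ICC 0 to 0.05; the last row is at ICC 0.05.

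**Variable takes.** Section 5.5 allows the take to differ by facility. If facilities recruit over a common window, takes are roughly proportional to confirmed cases. With the same total of 300 and suspected-load selection, Outcome 2 then occurs in about 9–12% of surveys for the 20% v 40% row and 12–16% for the 15% v 45% row. Combining confirmed-load selection with such takes counts positivity twice: Outcome 2 drops to about 1–6%, a downward bias.

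**The case against.** The strongest reply is that the link is not shown where it is needed. Section 5.5 relates deletions to transmission as a reason to stratify before choosing domains, and the masking remarks in section 5.6 concern domains and zones. Each domain is analysed on its own, so differences between areas do no harm. Facility positivity also depends on how much non-malarial fever is seen, so it is not the same as transmission. This stands: a reader might infer that the protocol itself asserts a within-domain link, and it does not. Section 4 does ask that facilities reflect the geographical spread of transmission across the domain, so variation within a domain is plausible, but it is not quantified.

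Second, the larger rates come from threefold contrasts in two aligned blocks of facilities. This also stands. Reading them against a nominal 5% would overstate them, because the rule itself yields about 6–9% at the threshold.

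Third, the fixed take is half of the mechanism and is not universal. Section 5.5 permits variable takes, an unspecified random procedure and sentinel sites; section 5.6 permits convenience sites. The suspected-case weighting belongs to the proportional-to-size route with a fixed take. That is still the route section 5.6 says should be used, and the representativeness warning is attached only to convenience sampling.

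Fourth, this is a template that countries tailor through their own procedures. That does not help if they copy the size measure that the template names.

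**Conclusion.** The mismatch follows from the text without assumptions: on this route the design weights suspected cases equally, the output is defined on confirmed cases, and the model does not adjust. Whether it biases a survey depends on a within-domain relation between positivity and deletion prevalence for which the protocol gives no figures. With no such relation there is no bias. With a mild contrast the effect is negligible. With two- to threefold contrasts in positivity, Outcome 2 at exactly 5% rises from about 6–9% to about 14–32%. With the opposite relation it falls to about 1% and power is lost.

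A reader might conclude that domains at 5% will generally be pushed into Outcome 2, or that Table 2 is wrong. Neither follows: the direction is not established, and Table 2 reproduces. The point is worth correcting because the remedy is small and the decision it protects is large.

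**What to change.** In section 5.6, step 1, replace the size measure by wording such as: *Where a fixed number of confirmed cases is taken at each facility, the sampling frame must include each facility's expected confirmed P. falciparum case load (suspected malaria case load multiplied by that facility's test positivity) and its type. This size measure should not be combined with takes proportional to case load, such as those from a common recruitment window.*

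Where facility positivity is not available before selection, or takes vary, add a sensitivity estimate of output 1 that weights each facility's cases by the inverse of their actual inclusion probability. For suspected-load selection with a fixed take, this is Σ q_i × (x_i / n_i) / Σ q_i. Here x_i / n_i is the facility's proportion of confirmed cases with a deletion-caused false negative, and q_i is confirmed over tested from the Annex 6 tally sheet. Report it beside the DRpower result. It should not be read as a point-estimate decision against 5%, because section 5.4 reserves that decision for the posterior probability.

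The cost is a few sentences and no extra patients or tests. Section 6 already asks planners to consider positivity at each facility, although the first bullet of step 1 speaks only of "the mean test positivity rate in the target area in order to ascertain the expected number of positive cases each week". The downside is that routine positivity is approximate and largely HRP2-based, so it slightly under-counts facilities with deletions. In the 15% v 45% example, HRP2 tests missing only the deletion cases would show 90% of cases in one group and 96.7% in the other, a ratio of 0.931. The low group's share becomes 0.25 × 0.931 / (0.25 × 0.931 + 0.75) = 0.237, and the mean under test 0.237 × 10% + 0.763 × 3.33% = 4.9%. This is far closer to 5% than the 6.67% under suspected-load selection.

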**Table 4. Available non-WHO-prequalified tests meeting critical criteriaa**

Product name	Product code	Manufacturer name
Biocredit Malaria Ag Pf (pLDH)	C14RHG25, C14RHH25	Rapigen Inc.
Biocredit Malaria Ag Pf (pLDH/HRP2)	C13RHG25, C13RHH25	Rapigen Inc.
Biocredit Malaria Ag Pf/Pv (pLDH/pLDH)	C61RHG25, C61RHH25	Rapigen Inc.
CareStart™ Malaria Pf (HRP2/pLDH) Ag RDT	RMPM-02571	Access Bio Inc.
CareStart™ Malaria PAN (pLDH) Ag RDT	RMNM-02571	Access Bio Inc.

a Valid ISO 13485:2003, submission of application for WHO prequalification, and acceptable diagnostic performance against both HRP2-expressing and non-HRP2-expressing at 200 parasites/μL (*pfhrp2/3* single or double deletions), based on the most recent WHO laboratory assessment performed at the United States Centers for Disease Control and Prevention.

- For each consenting suspected malaria case, the health provider will attach a unique survey ID, chronologically ordered, to a survey case report form (Annex 7) and to the survey tally sheet (Annex 6). On the survey case report form, the health worker will record answers to questions regarding age, sex, and recent history of malaria diagnostic testing, treatment and travel.
  - Next, using the labels attached to the survey case report form (with the same ID number as the form), the health worker (treating clinician or laboratory worker) will label two different RDTs or one RDT and microscopy slide and a filter paper or protein saver card for DBS. The health worker will perform the tests, record the results on the survey case report form (Annex 7, sections 5–7), and either inform the patient of the results directly (clinician) or refer (laboratory worker) the patient back to the treating clinician for treatment in the case of positive test results on the primary or secondary RDT, or microscopy as per national guidelines. Results from either RDT should be acted upon, as both are WHO-prequalified. Microscopy is also considered an acceptable alternative to malaria RDTs. Negative RDT results should be managed as per national guidelines.
3. All used RDTs and, if applicable, microscopy slides from each consenting suspected malaria case will be stored until the survey is complete in a dry and protected area for survey quality control purposes.
  4. A minimum of two DBSs (50 µL per spot) on filter paper or protein saver card will be placed in a clean, dry and protected area and allowed to dry for 3–4 hours. Once dry, the filter paper/cards will be placed with the desiccant (from the RDT package) in a gas-impermeable plastic bag labelled with the survey ID if it is not stuck directly on the filter paper.
  5. Once the desired sample size of infected consenting individuals has been obtained at each facility, the survey case report forms and corresponding RDTs and DBSs should be compiled and sent to the central coordinating centre. No names or other unique identifying information should be contained on the forms, tally sheets, RDTs or DBSs. The only link between patient name and survey ID number should be on the consent form of the consenting individuals.
  6. Upon receipt of the forms, RDTs and DBSs, the survey team supervisor must review the RDT results section of the report form (Annex 7, section 5–7, S1 ), and determine which DBSs to prioritize for molecular +/- serological analysis (specifically, those that are HRP2 RDT negative and Pf-LDH or microscopy positive, and depending on resources, also a subset of HRP2 positive and negatives; see Annex 1) and which to discard.

Based on the number of discordant RDT or RDT-microscopy results, one can calculate the proportion of *P. falciparum* cases with suspected false-negative HRP2 RDT results (indicating potential *pfhrp2/3* gene deletions) in the health facility or domain (primary output indicator 2), using the formula below.

$$\text{Proportion of } P. \text{ falciparum} \text{ cases with suspected } pfhrp2/3 \text{ deletions} = \frac{\text{\# of } P. \text{ falciparum} \text{ cases with discordant RDT (HRP2- / Pf-LDH+) or discordant RDT-microscopy (HRP2- / microscopy+) results}}{\text{\# of confirmed } P. \text{ falciparum} \text{ cases (positive by Pf-LDH RDT or microscopy)}}$$

7. The DBSs (minimum of two) will be packaged and shipped for *P. falciparum* confirmatory testing and molecular +/- serological analysis for *pfhrp2/3* gene deletions to a WHO collaborating reference laboratory. Samples should be shipped under a material transfer agreement. Ideally, if more than two DBSs were collected, one DBS will remain in the survey country's reference laboratory at all times.
  - Molecular-based confirmation of *pfhrp2/3* deletions is needed to ensure that discordant results are caused by *pfhrp2/3* gene deletions and not by other factors, such as operator error, false-positive Pf-LDH test lines, false-positive microscopy results, or samples at the limit of detection of the RDTs, which may not always react sufficiently to generate a positive test line. The contribution of these alternative causes of discordant results will vary.
  - Serological confirmation of *pfhrp2/3* gene deletions may also be performed using immunoassays, especially on samples where there is lack of agreement between RDT and PCR results.
8. Once the true number of cases with false-negative HRP2 RDT results caused by *pfhrp2* gene deletions is known, the prevalence at the domain level can be calculated for each sampling domain (e.g. province, state), using the DRpower software or interactive web app (<https://shiny.dide.ic.ac.uk/DRpower-app/>). This software also calculates a 95% CrI around this estimate (see Annex 3). The raw calculation is based on the formula:

$$\text{Proportion of } P. \text{ falciparum} \text{ cases with false-negative HRP2 RDT results due to } pfhrp2/3 \text{ deletions} = \frac{\text{\# of confirmed } P. \text{ falciparum} \text{ cases with } pfhrp2/3 \text{ gene deletions and HRP2-RDT negative results}}{\text{\# of confirmed } P. \text{ falciparum} \text{ cases (positive by either Pf-LDH RDT or microscopy)}}$$

9. Statistical analysis in DRpower will also result in an estimate of the probability that the prevalence of false-negative HRP2 RDT results caused by *pfhrp2/3* gene deletions is above 5%. This will result in one of two outcomes per domain:

**Outcome 1:** The posterior probability of being above the 5% threshold is less than 0.95. In this case, there is not sufficient evidence to conclude that the proportion of false-negative RDT results caused by *pfhrp2/3* gene deletions among symptomatic *P. falciparum* patients is greater than 5%.

**Outcome 2:** The posterior probability of being above the 5% threshold is greater than or equal to 0.95. In this case, there is high statistical confidence that the proportion of false-negative HRP2 RDT results caused by *pfhrp2/3* gene deletions among symptomatic *P. falciparum* patients is greater than 5%.

10. If outcome 2 is obtained in any domain, the country programme should make a nationwide switch to RDTs that do not rely solely on HRP2 for detecting *P. falciparum*, prioritized on the basis of the prevalence of false-negative HRP2 RDT results caused by *pfhrp2/3* deletions across domains.
  - A threshold of 5% was selected because it is somewhere around this point that the proportion of cases missed by HRP2 RDTs due to non-HRP2-expressing parasites may be greater than the proportion of cases that would be missed by less-sensitive pLDH-based RDTs.
  - A nationwide change is suggested because mathematical models show that parasites lacking *pfhrp2* genes will spread (31) under HRP2-only RDT pressure and because the use of multiple RDTs in a country can complicate procurement and training practices.

11. If outcome 1 is obtained in all domains, it is recommended that the country establish a monitoring mechanism whereby this survey is repeated in two years (or sooner).
12. Once the results of the survey have been finalized and reported, only the DBSs from consenting individuals (denoted on the DBS itself), the plastic bag and case report form should be kept for long-term storage. All other materials associated with the survey (RDTs, microscopy slides and DBSs) should be discarded. Consent forms linking patient names to survey IDs should be maintained by the Ministry of Health. The biobank holder should not possess the information linking patient IDs to samples.
13. All activities should be carried out under the supervision of the principal investigator. A dedicated study coordinator should be identified. It is recommended that there be a minimum of one supervisor per domain where the survey is to be undertaken. One to two survey staff should be trained in each selected survey health facility to record the results of malaria diagnostic testing for all suspected malaria cases, enrol survey participants for long-term sample storage according to the protocol, collect RDTs and/or microscopy slides, collect DBSs on filter paper, conduct the questionnaire interviews, and properly store and package all samples/report forms for shipment to the laboratory. Either the supervisor or person with the requisite expertise should manage the data after collection, create indicator variables and analyse the data. Ideally, this should be done at the central level.

